## 8.0 Criteria for Evaluation and Endpoint Definitions

- 8.1 The primary end-point is taken as difference in tumor-specific immune response (comparing before and after treatment with BCG). Tumor-specific immune response will be measured using a standard T cell proliferation assay. T cell response to autologous tumor will be measured using a paired analysis by utilizing PBMCs collected before and after BCG therapy. Autologous monocyte-derived dendritic cells (moDCs) and autologous T cells will be co-cultured following pulsation of moDCs with whole tumor lysates.
- 8.2 Secondary endpoints are exploratory and will not be considered for determining sample size. Secondary endpoints include (1) description of tumor infiltrating lymphocyte populations following BCG (examining 3 weeks of treatment versus 4,5, or 6 weeks as available); (2) determination of the presence/absence of BCG in lymph nodes following treatment; (3) examining extent of necrosis/apoptosis in tumor following BCG treatment; (4) pathologic assessment of tumor stage following BCG treatment; (5) characterization of systemic immune populations before treatment, at time of cystectomy,

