### **Study Schema**

## 1.0 Objectives

1.1 The primary objectives of the study are to determine:

- a. the ability of intravesical BCG immunotherapy to enhance tumor-specific immunity as measured by autologous T cells proliferation following co-culture with autologous monocyte-derived dendritic cells pulsed with autologous tumor lysate

1.2 Secondary objectives of the study are to determine:

- a. the immune effects of BCG in the tumor microenvironment and tumor-draining lymph nodes
- b. the extent to which BCG is processed and presented by tumors cells and/or antigen-presenting cells
- c. the ability of BCG to elicit tumor necrosis/apoptosis in invasive disease
- d. the pathologic stage of disease following BCG treatment
- e. to determine if immune changes elicited by BCG in patients with bladder cancer will provide an opportunity for benefit from mTOR inhibition in tumor milieu

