## 9.0 Statistical Considerations

### 9.1 Sample Size Determination

This is a one-arm open label study of the tumor-specific immune effect of BCG in participants undergoing radical cystectomy for bladder cancer. The sample size calculation is based on one-sided testing on the proportion of subjects who experience an increase in T cell proliferation ( $\geq 100\%$  increase in proliferative index during the proliferation assay) in post treatment assessment compared to pretreatment assessment with power=90% and target alpha=5%. The null proportion responding is taken to be 0.10 and the desired proportion responding is specified as greater than or equal to 0.50. The estimated sample size, under these assumptions, is 10. In order to achieve this number

we would need to consent 25 participants to account for completion rate and assay variability.

Sample size calculations were run using Stata 10.1 (College Station, Texas).

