#### Data analysis

Descriptive graphs will be developed to describe immune subpopulations and immunodynamic end points on paired samples on an intraindividual basis. For all other immune analyses, comparisons between groups will be conducted using the nonparametric Wilcoxon rank-sum test and comparison within groups will be conducted using the Wilcoxon signed-rank test. Correlation will be analyzed with the Spearman rank test.

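### At ten evaluable patients no success count delivers the 5% alpha and 90% power stated in 9.1, and the plan names neither the test of the responder proportion nor the number of responders needed.

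*Combined protocol and SAP*

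**What the plan says.** Objective 1.1 is to determine "the ability of intravesical BCG immunotherapy to enhance tumor-specific immunity as measured by autologous T cells proliferation" after co-culture with lysate-pulsed dendritic cells. Section 8.1 turns this into an endpoint: "The primary end-point is taken as difference in tumor-specific immune response (comparing before and after treatment with BCG"), analysed as paired samples. Neither place gives a threshold or a proportion.

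Section 9.1 is more specific. It bases the sample size on "one-sided testing on the proportion of subjects who experience an increase in T cell proliferation", defines the increase as a rise of at least 100% in proliferative index, and compares patients "in post treatment assessment compared to pretreatment assessment with power=90% and target alpha=5"%. The null proportion is 0.10 and the desired proportion is 0.50 or more. It concludes: "The estimated sample size, under these assumptions, is 10". It adds that 25 participants would need to be consented to allow for completion rate and assay variability.

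The Data analysis paragraph opens with descriptive graphs and then says: "For all other immune analyses, comparisons between groups will be conducted using the nonparametric Wilcoxon rank-sum test", while "comparison within groups will be conducted using the Wilcoxon signed-rank test". It names no test of a proportion and no number of responders that counts as success.

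Research blood is drawn twice after BCG: at cystectomy (6.4) and at the follow-up visit within about 90 days of surgery (6.5). Neither 8.1 nor 9.1 says which draw supplies the post-treatment value.

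**The concern.** With about ten patients the responder count moves in coarse steps, and each step changes the error rates a good deal. A plan that quotes alpha and power but gives no success count leaves the decision rule open, and here the open choice matters. Three responders in ten is the borderline result: one standard test calls it positive and another calls it negative. If the test is chosen after the data are seen, that choice could settle the trial's conclusion.

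The stated 5% and 90% are also not the operating characteristics of any rule the trial could apply at ten patients, so a reader of 9.1 would have the wrong picture of the design.

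**Working it through.** **Inputs, all from 9.1.** One-sided alpha 0.05 (z = 1.645), power 0.90 (z = 1.282), p0 = 0.10, p1 = 0.50, ten evaluable, 25 consented.

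**1. Reproduce the plan's ten.**
- Normal approximation: n = [(1.645·√(0.10·0.90) + 1.282·√(0.50·0.50)) / 0.40]² = [(0.493 + 0.641)/0.40]² = 8.04, rounded up to 9.
- Arcsine: n = [(1.645 + 1.282) / (2·(arcsin√0.50 − arcsin√0.10))]² = (2.926/0.927)² = 9.96, rounded up to 10.
- One-sided normal with continuity correction: 10.39, rounded up to 11.

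The stated ten therefore agrees with large-sample formulas. On the uncorrected normal approximation, power at n = 10 is 93.9%.

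**2. Exact probabilities at n = 10.**
- Under 0.10: P(0) = 0.3487, P(1) = 0.3874, P(2) = 0.1937, P(3) = 0.0574. So P(≥3) = 1 − 0.9298 = 0.0702 and P(≥4) = 0.0702 − 0.0574 = 0.0128.
- Under 0.50: P(≥3) = 1 − (1+10+45)/1024 = 0.9453 and P(≥4) = 0.9453 − 120/1024 = 0.8281.

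| Success at n = 10 | Alpha | Power |
|---|---|---|
| ≥2 | 26.4% | 98.9% |
| ≥3 | 7.0% | 94.5% |
| ≥4 | 1.3% | 82.8% |
| ≥5 | 0.2% | 62.3% |

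No row has alpha at or below 5% together with power at or above 90%.

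**3. The borderline result, 3 of 10.**
- Uncorrected z: (0.30 − 0.10)/√(0.09/10) = 2.108, one-sided p = 0.018: positive.
- Continuity-corrected z: (0.20 − 0.05)/0.0949 = 1.58, below 1.645: negative.
- Exact binomial: p = 0.070: negative.

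The uncorrected z test is thus the ≥3 rule, with true alpha 7.0%. The other two are the ≥4 rule, with power 82.8%.

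**4. Where both targets are met.** For each evaluable number, take the smallest success count with exact alpha at or below 5%:

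| Evaluable | Success | Alpha | Power |
|---|---|---|---|
| 5 | ≥3 | 0.9% | 50.0% |
| 8 | ≥3 | 3.8% | 85.5% |
| 9 | ≥4 | 0.8% | 74.6% |
| 10 | ≥4 | 1.3% | 82.8% |
| 11 | ≥4 | 1.9% | 88.7% |
| 12 | ≥4 | 2.6% | 92.7% |
| 14 | ≥4 | 4.4% | 97.1% |
| 15 | ≥5 | 1.3% | 94.1% |
| 20 | ≥5 | 4.3% | 99.4% |
| 21 | ≥6 | 1.4% | 98.7% |
| 25 | ≥6 | 3.3% | 99.8% |

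Both targets are first met at 12 and are met at every number from 12 to 25.

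**The case against.** The strongest reply is that 9.1 already carries most of a primary analysis: readout, per-patient threshold, pre/post contrast, direction, both proportions, alpha and power. It speaks of a target alpha and an estimated sample size, and ten follows from accepted formulas. Missing nominal levels at ten patients is ordinary discreteness in a small mechanistic study. All of that stands, and it rules out several stronger readings that a reader might infer:

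- *That ten is a miscalculation.* It reproduces. The gap is between the large-sample levels and what a count of ten can deliver.
- *That the responder is undefined.* The 100% threshold is in 9.1. What is missing is the number of responders needed.
- *That 8.1 and 9.1 set up rival primary endpoints, or that the signed-rank test is the primary test.* A doubling within a patient is itself a paired comparison, so 9.1 can be read as making 8.1 operational. Section 8.2 says "Secondary endpoints are exploratory and will not be considered for determining sample size", which points to the 9.1 proportion as primary. The Wilcoxon sentence covers the other immune analyses and most naturally leaves the primary out.
- *That the post-BCG sample is unknowable.* The pre-surgical design, with blood and tissue taken together at cystectomy, makes that draw the likelier one.
- *That the trial cannot reach 90% power.* Ten is the planned evaluable number, not a cap, and 25 are to be consented.

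It may also be said that the exact test is a matter of taste. In part it is: any test named in advance would remove the ambiguity. But the uncorrected z test has a true alpha of 7.0%, above the plan's own 5%, and at n = 10 the corrected z test gives the same rule as the exact test.

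The reply does not supply the name of the test or the success count, and it does not make 5% and 90% true at ten.

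**Conclusion.** The point holds in this limited form. At ten evaluable patients the design has either alpha 7.0% with power 94.5% or alpha 1.3% with power 82.8%, depending on a success count the plan does not state. A rule that respects 5% has 83% power, about seven points below the stated 90%. Three responders in ten would be read either way. This rests only on the 9.1 inputs and on independent patients with a common response probability.

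That 8.1 omits the responder proportion and that the post-BCG draw is unnamed are secondary clarifications, since context favours the proportion and the cystectomy sample. The draw still deserves a sentence: the later sample follows tumour removal, so a change there could not be put down to BCG alone.

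The correction should be made before the primary data are analysed.

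**What to change.** **Data analysis.** State that the single primary analysis is an exact one-sided binomial test of the responder proportion against 0.10 at 5%, with success at ≥3 of 5–8, ≥4 of 9–14, ≥5 of 15–20 or ≥6 of 21–25 evaluable patients. Signed-rank results and the post-cystectomy sample are supportive.

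**9.1.** Restate power at ten evaluable as 83% (alpha 1.3%). Note that 5%/90% is first met at 12 evaluable (≥4 of 12: 2.6%/92.7%) and holds from 12 to 25, within the number to be consented. Commit to reporting power for the number reached.

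**8.1.** State the primary endpoint as the proportion of evaluable patients with a rise of at least 100% in proliferative index from the pre-BCG sample to the cystectomy sample. Define evaluable as having valid paired assays and autologous tumour lysate.

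**Cost.** Wording only, with no new visits or samples. The downsides are:
- Stated power at ten falls from 90% to 83%.
- Power is not monotone in the evaluable number (50% at 5, 85.5% at 8, 74.6% at 9). The sponsor should decide whether a formal claim from very few patients is wanted.
- 90% power needs 12/25 = 48% evaluable, against 10/25 = 40% for the stated ten. The documents give no observed evaluable rate. At an assumed 40%, 50% or 60%, the binomial chance of reaching 12 of 25 is 27%, 65.5% or 92%, against 58%, 89% or 99% for reaching ten.
- The wording does not cure two limits on the evaluable number: baseline research blood is optional (6.2.1), and tumour is taken only where there is excess (6.4).

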## 9.0 Statistical Considerations

### 9.1 Sample Size Determination

This is a one-arm open label study of the tumor-specific immune effect of BCG in participants undergoing radical cystectomy for bladder cancer. The sample size calculation is based on one-sided testing on the proportion of subjects who experience an increase in T cell proliferation ( $\geq 100\%$  increase in proliferative index during the proliferation assay) in post treatment assessment compared to pretreatment assessment with power=90% and target alpha=5%. The null proportion responding is taken to be 0.10 and the desired proportion responding is specified as greater than or equal to 0.50. The estimated sample size, under these assumptions, is 10. In order to achieve this number

we would need to consent 25 participants to account for completion rate and assay variability.

Sample size calculations were run using Stata 10.1 (College Station, Texas).

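### Ten evaluable patients cannot give both 90% power and a one-sided 5% error: the exact test has 82.8% power, or a 7.0% type I error if the cut-off is relaxed

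*Combined protocol and SAP*

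**What the plan says.** Section 9.1 (Sample Size Determination) sets out the calculation: "The sample size calculation is based on one-sided testing on the proportion of subjects who experience an increase in T cell proliferation". A responder is a patient whose proliferative index at least doubles between the pre- and post-treatment assays. The error rates and null value are given as "compared to pretreatment assessment with power=90% and target alpha=5%. The null proportion responding is taken to be 0.10", and for the alternative "the desired proportion responding is specified as greater than or equal to 0.50". The result is: "The estimated sample size, under these assumptions, is 10".

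To reach that number, "we would need to consent 25 participants to account for completion rate and assay variability". On method, 9.1 says only "Sample size calculations were run using Stata 10.1 (College Station, Texas". It does not say whether the test is exact or approximate, how many responders count as success, or what error rates the chosen design attains. The Data analysis text that follows names descriptive graphs, Wilcoxon tests and Spearman correlation. It names no test of a responder proportion.

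**The concern.** With 10 patients the responder count can take only 11 values, so the attainable type I error moves in large steps. A formula that treats the count as continuous can return a sample size at which no real decision rule has the stated properties. At 10 patients and a null rate of 0.10 the expected number of responders is 10 × 0.10 = 1, which is far too few for a normal approximation.

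The responder comparison is the only hypothesis on which the study is sized; section 8.2 makes the secondary endpoints exploratory and leaves them out of the sizing. If its stated power or error rate is wrong, the one quantitative justification for the design is wrong. The missing cut-off adds a practical problem. Three responders out of 10 is a quite possible result, and whether it counts as positive depends on a choice that could be made after the data are seen in an open-label, single-arm study.

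**Working it through.** **Inputs, all from section 9.1.** One-sided test of a single proportion; α = 0.05; power = 0.90; p0 = 0.10; p1 = 0.50; evaluable n = 10; consented n = 25.

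**Step 1: where the 10 comes from.** The usual normal formula is

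n = [(z_α √(p0(1−p0)) + z_β √(p1(1−p1))) / (p1−p0)]²,

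with √(0.10 × 0.90) = 0.3, √(0.50 × 0.50) = 0.5, p1 − p0 = 0.4 and z_β = 1.2816.

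- One-sided 5% (z = 1.6449): [(0.4935 + 0.6408)/0.4]² = 8.04, rounded up to 9.
- One-sided with continuity correction: 9.25 or 10.39 depending on the form of the correction, rounded up to 10 or 11.
- One-sided arcsine: [(1.6449 + 1.2816)/0.9273]² = 9.96, rounded up to 10.
- Two-sided 5% (z = 1.9600): [(0.5880 + 0.6408)/0.4]² = 9.44, rounded up to 10. The plan specifies one-sided, so this route would not match its own text.

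So 10 can be reproduced, but only from large-sample formulas.

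**Step 2: exact error rates at n = 10.** For a rule that declares success at r or more responders, α = P(X ≥ r | 10, 0.10) and power = P(X ≥ r | 10, 0.50).

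- Under 0.10, the probabilities of 0, 1, 2 and 3 responders are 0.3487, 0.3874, 0.1937 and 0.0574.
- Under 0.50, they are 1, 10, 45 and 120, each divided by 1024.

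| Success rule | Type I error | Power at 0.50 |
|---|---|---|
| ≥3 of 10 | 1 − 0.9298 = 7.02% | 1 − 56/1024 = 94.5% |
| ≥4 of 10 | 1 − 0.9872 = 1.28% | 1 − 176/1024 = 82.8% |

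A lower cut-off raises the type I error further and a higher one lowers the power further. No cut-off meets both targets.

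**Step 3: what an approximate test would do.** At 3 of 10, z = (0.30 − 0.10)/√(0.09/10) = 2.11, above 1.645, so the uncorrected z test rejects and its true error is 7.02%. With a continuity correction, z = (0.30 − 0.05 − 0.10)/√0.009 = 1.58, so it does not reject; the rule becomes ≥4 and power is 82.8%. The two versions disagree at exactly 3 of 10, a result with probability 120/1024 = 11.7% when the true rate is 0.50.

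**Step 4: smallest n meeting both targets exactly.**

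| Evaluable n | Cut-off | Type I error | Power at 0.50 |
|---|---|---|---|
| 10 | 4 | 1.28% | 82.8% |
| 11 | 4 | 1.85% | 88.7% |
| 12 | 4 | 2.56% | 92.7% |

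For every n from 12 to 25, the exact 5% rule has power above 90%. The exact cut-offs are 3 for n = 5–8, 4 for n = 9–14, 5 for n = 15–20 and 6 for n = 21–25.

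**The case against.** The best defence is that 10 is not a slip. Standard approximations give it, the text calls it an estimate, and it speaks of a target alpha. That explains the figure. It does not make the stated power and error rate true, because any fixed rule on 10 patients must use one of the cut-offs above. Nor does the plan report an attained error of 7%, so nothing shows that 7% was accepted.

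A second argument is that the shortfall is small: two evaluable patients, in a mechanistic study that never calls this test confirmatory. The plan also allows a true rate above 0.50, and with the ≥4 rule power reaches about 90% at a rate of 0.55 (89.8%). With that rule there is no false-positive problem, since the error is 1.28%. All of this is fair. Even so, the power is claimed at 0.50, and there the type II error is 17.2%, not 10%.

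Third, section 8.1 describes a paired before/after comparison and the Data analysis text names no responder test, so the dispute over 3 of 10 might never arise. That is a further gap in the plan, and it does not rescue 9.1, which sizes the study on the proportion.

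Finally, reaching 12 evaluable from 25 consented needs 12/25 = 48%, while the plan's own ratio is 10/25 = 40%. If each patient were evaluable independently with probability 40% (an assumption), the chance of 12 or more would be about 27%. This stands, and it limits what the fix can promise.

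**Conclusion.** The concern holds. At 10 evaluable patients the design does not have the properties that 9.1 states. Keeping the one-sided error at or below 5%, power is 82.8%, a shortfall of 7.2 percentage points from 90%. Keeping power at 90% or more, the one-sided error is 7.02%. Both targets are first met together at 12 evaluable patients.

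These are exact binomial results at p0 = 0.10 and p1 = 0.50. They assume independent patients and a fixed success cut-off, and they do not depend on which named test was intended. This should be corrected before analysis, because it misstates the operating characteristics of the only sized test and leaves the success rule open.

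**What to change.** In section 9.1:

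- Name an exact one-sided binomial test of a responder rate of 0.10 at the 5% level.
- For 10 evaluable patients, define success as 4 or more responders, and state the attained type I error (1.3%) and power at 0.50 (83%).
- Because the evaluable number will vary, fix the cut-off for each: 3 for n = 5–8, 4 for n = 9–14, 5 for n = 15–20, 6 for n = 21–25.
- State that power reaches 90% only if 12 or more of the 25 consented are evaluable.

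Repeat the test and cut-offs in the Data analysis text, so that the analysis performs the test on which the study was sized.

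The cost is wording and a less favourable power statement. The restatement needs no extra enrolment. If the sponsor would rather plan for 90% power, the target is 12 evaluable; at the plan's 40% ratio that means consenting 12/0.40 = 30.

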#### Data analysis

Descriptive graphs will be developed to describe immune subpopulations and immunodynamic end points on paired samples on an intraindividual basis. For all other immune analyses, comparisons between groups will be conducted using the nonparametric Wilcoxon rank-sum test and comparison within groups will be conducted using the Wilcoxon signed-rank test. Correlation will be analyzed with the Spearman rank test.

#### 10.0 Registration Guidelines

Participants will be registered on to IDEAS.

#### 11.0 Ethical and regulatory

The following must be observed to comply with Food and Drug Administration regulations for the conduct and monitoring of clinical investigations; they also represent sound research practice:

##### Informed Consent

The principles of informed consent are described by Federal Regulatory Guidelines (Federal Register Vol. 46, No. 17, January 27, 1981, part 50) and the Office for Protection from Research Risks Reports: Protection of Human Subjects (Code of Federal Regulations 45 CFR 46). They must be followed to comply with FDA regulations for the conduct and monitoring of clinical investigations.

##### Institutional Review

This study must be approved by an appropriate institutional review committee as defined by Federal Regulatory Guidelines (Ref. Federal Register Vol. 46, No. 17, January 27, 1981, part 56) and the Office for Protection from Research Risks Reports: Protection of Human Subjects (Code of Federal Regulations 45 CFR 46).

#### 12.0 Data and Safety Monitoring Oversight

A Data and Safety Monitoring Plan (DSMP) is required for all an individual protocols conducted at CTRC. All protocols conducted at CTRC are covered under the auspices of the CTRC Institutional Data Safety Monitoring Plan.

The CTRC Institutional DSMP global policies provide individual trials with:

- institutional policies and procedures for institutional data safety and monitoring,
- an institutional guide to follow,
- monitoring of protocol accrual by the CTRC Protocol Review Committee,
- review of study forms and orders by the Forms Committee,
- tools for monitoring safety events,
- monitoring of UPIRSO's by the Director of Quality Assurance and DSMC,
- determining level of risk (Priority of Audit Level Score – PALS) ,
- oversight by the Data Safety Monitoring Committee (DSMC), and
- verification of protocol adherence via annual audit for all Investigator Initiated Studies by the CTRC Quality Assurance Division.

##### Monitoring Safety:

Due to the low risk associated with participation in this protocol, the Principal Investigator will perform primary assessment of adverse events, adverse event trends and treatment effects on this study. The PI will conduct independent review and report findings yearly to the CTRC Data Safety Monitoring Committee (DSMC) and the UTHSCSA IRB.

Baseline events and adverse events will be captured using the CTRC Master Adverse Events Document for each patient using CTCAE V. (specify version you will use in this protocol) for the grading and attribution of adverse events. Usage of the CTRC Master Adverse Events Document centrally documents:

- the event and grades the seriousness of it,
- if the event was a change from baseline,
- determines the relationship between the event and study intervention,
- if the event was part of the normal disease process, and
- what actions were taken as a result of the event.

